10.4.2.1 Secondary Effectiveness Endpoints

- Procedure success rate

The number and percentage of subjects who achieved procedure success will be summarized at immediately post-treatment (acute), 6-Month and 12-Month Follow-up visits.

- Rate of complete aneurysm occlusion

The number and percentage of subjects who have achieved complete aneurysm occlusion at immediately post-procedure (acute) and 6-Month Follow-up will be summarized based on the assessment from the Independent Core Laboratory.

- Complete/partial aneurysm occlusion as per the Raymond scale

The number and percentage of subjects who have reported a Raymond score of 1 (complete obliteration) or 2 (residual neck) will be summarized at immediately post-treatment (acute), 6-Month and 12-Month Follow-up Visits, based on the assessment from the Independent Core Laboratory.

- Percent aneurysm occlusion

The number and percentage of subjects by categories of aneurysm occlusion in percentage will be summarized at immediately post-procedure (acute), 6-Month and 12-Month Follow-up visits, based on the assessment from the Independent Core Laboratory.

- Recanalization rate

The number and percentage of subjects with recanalization up to and including 12-Month Follow-up Visit will be summarized based on the assessment from the Independent Core Laboratory.

- Retreatment rate

The number and percentage of subjects who received retreatments to the target aneurysms at any time up to and including 12-Month Follow-up will be summarized based on site reported data.

10.4.2.2 Secondary Safety Endpoints

- Rate of new neurological deficits as per mRS

The number and percentage of subjects with new neurological deficits, not related to stroke or death, will be summarized at baseline (pre-procedure) and follow-up visits, e.g., 30 days, 6 and 12 months post-procedure. Subjects who died prior to an evaluation will have an mRS score of 6 imputed at that timepoint for analysis purpose.

- NIHSS total score

The NIHSS total score and its change from baseline will be summarized at baseline (pre-procedure) and follow-up visits (6 months and 12 months post-procedure). In addition, the number and percentage of subjects who show a worsening from baseline (an increase of 4 points or more) will also be presented. Only the observed scores will be included in summaries.

- Adverse Events and Clinical Complications

AEs from the start of the index procedure until completion of the 12-Month Follow-up will be coded using the latest version of Medical Dictionary for Regulatory Activities (MedDRA) into system organ class (SOC) and preferred terms (PTs). The number of events, the number and percentage of subjects with events and event rates by SOC and PT will be summarized for the following:

- Any AEs
- Study device or procedure related AEs
- Any serious AEs (SAEs)
- Unanticipated AEs
- AEs leading to death

AEs related to device/procedure are defined as those with the relationship of definitely, probably or possibility related. AEs with miss relationship will not be imputed. Subjects with multiple relationships on the same AE will be reported by the events of the highest relationship. Only the relationship as determined by CEC will be used in the safety analysis.

In addition, device or procedure related AEs will be presented overall and by study period as follows:

Table 2: AEs by Study Period

Study Period	Lower Bound of AE Start Date	Upper bound of AE Start Date
Peri-procedure	from the beginning of the procedure	Until 24 hours post-procedure (Day 0)
12-Month Follow-up	After 24 hours post-procedure (i.e., from Day 1)	Until the date of: 
○ early discontinuation in the study; or

Study Period	Lower Bound of AE Start Date	Upper bound of AE Start Date
		
 ○ the upper bound of the 12-Month analysis window (i.e., Day 450)

If the AE onset day is missing but the month and year is available, then the missing day will be imputed to be Day 1 of that month as a conservative approach. As an example, if the AE has an onset date of July of 2016, with an unknown day, the imputed onset day would be 01JUL2016. If the month and/or year is unknown, then, the AE will be categorized as unknown.

- Reduced TICI Flow

The number and percentage of subjects with a reduced TICI flow (TICI score of 0 or 1) at the target vessel during the index procedure will be summarized. Subjects with missing data on this endpoint will be excluded from analysis.

- Bleeding complications

The number and percentage of subjects who experience a procedure-related hemorrhagic event which requires any of the following will be summarized:

- Blood transfusion
- Surgical intervention
- New hospitalizations
- Lengthening of hospital stay for the index procedure
- In-stent stenosis

The number and percentage of in-stent stenosis at immediately post-procedure (acute), and up to and including 6-Month Follow-up (excluding acute events) will be summarized in the same way the primary safety endpoint (in-stent stenosis) at 12-Month Follow-up.

For subjects with acute in-stent stenosis, the number and percentage of subjects who have parent vessel stenosis caused by vasospasm, and whether vasospasm was responsive to medication will be summarized based on the assessment from the Independent Core Laboratory.

- Thrombosis

The number and percentage of subjects with thrombosis up to and including 6 months and 12 months post-procedure will be summarized based on the assessment from the Independent Core Laboratory. Subjects with missing data on thrombosis will be excluded from analysis.

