## SCHEDULE OF EVENTS

Table 1: Summary of Study Procedures and Assessments

Assessments	Screening/ Baseline (-14 to 0 days)	Pre-treatment  (day 0)	Intra-procedure  (day 0)	Post-treatment  (day 0)	Angiographic Screening Failure  (day 0)	Hospital discharge 	30 Days (16 - 44 days)	6 Months (92-212 days)	12- Months (320-410 days)	18 Months (457-592 days)	24 Months  (685-775 days)	Stroke or Suspected Stroke 
Study approved informed consent	X											
Medical history	X											
Clinical assessment & physical exam	X					X		X	X		X	
NIH Stroke Scale Score (NIHSS)	X					X 		X	X		X	X
Modified Rankin Scale (mRS)	X					X 	X	X	X	X	X	X
Clinical neurological evaluation	X					X 	X	X	X	X	X	
Hunt and Hess Scale (HHS) for subarachnoid hemorrhage						X 		X	X		X	
Vital Signs	X	X		X	X	X		X	X		X	
Relevant prior and concomitant medications 	X					X	X	X	X	X	X	
Serum creatinine	X											
Pregnancy test 	X											
Index Procedure			X									
Procedural Medications 		X	X	X	X							
Imaging:												
CT or MRI performed within 10 years 	X 											
Angiogram 	X 	X	X	X 	X			X	X		X	
MRI/MRA or Angiogram											X 	
MRI for Stroke/Suspected Stroke (within 24 hrs.)												X
Record of adverse events 		X	X	X	X	X	X	X	X	X	X	
Record of protocol deviation 	X	X	X	X	X	X	X	X	X	X	X	
Record device malfunction/product complaint 		X	X	X		X	X	X	X	X	X	
End of Study (occurring once at any timepoint)		X	X	X	X	X	X	X	X	X	X	

1. At 12 to 36 hours after end of the index procedure.

2. Procedural and relevant concomitant medications include: Antithrombotic (including anti-platelet, anticoagulant, and fibrinolitics), inhibitors of ADP-induced platelet aggregation, IIb-IIIa Inhibitor, vasoactive medications, contrast and medication associated with AEs.

3. For females of childbearing potential as assessed per investigator.

4. As needed.

5. Collect at the index procedure and any subsequent procedures, if applicable.

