### **6.1.3 Baseline Medication and Assessments**

The following pre-procedure medications are a requirement of this protocol. Confirmation of correct antiplatelet therapy prior to the procedure must be documented. If confirmation of the correct antiplatelet therapy is not available, the procedure should be delayed.

- Aspirin (ASA): At least 81 mg/day for a minimum of 7 days prior to the procedure
- P2Y12 Platelet Inhibitor: Daily for a minimum of 7 days prior to the procedure

All patients must have platelet reactivity testing performed. Record the test results in the applicable eCRF.

The following baseline data must be collected for all subjects prior to the treatment procedure (within 14 days prior to index procedure). Note that the study informed consent must be signed prior to any study protocol required assessments or procedures that are not routine standard of care by the investigation.

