#### **9.10.4 Analysis of Angiographic Screening Failures**

Data will be collected from the time of consent through a 72-hour safety evaluation or hospital discharge (whichever comes first) or, in the case of an AE that has not resolved by 72 hours post-angiogram or discharge, the resolution of the AE. Demographics, baseline subject and aneurysm characteristics, procedural and safety data will be listed and summarized separately from the other analysis populations.

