### **10.5.2 Adverse Event Reporting for Entered Subjects**

The adverse event reporting period for this study begins at the time the study informed consent is signed and ends at the twenty-four month follow-up unless noted otherwise in Section 11.3. Adverse events that occur in subjects during the adverse event reporting period must be entered into the eCRF database. All required treatments and outcomes of the adverse event must be recorded.

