5.4 Safety Follow-up after 12 Months Post-Procedure

According to the Close Out Plan, all enrolled and treated subjects will be required to complete follow-up visits through 12 months post-procedure. Hence, only a small number of subjects will have additional safety follow-up data post 12 months. AEs that started after 12-month follow-up will only be listed.

6. Levels of Significance

Protocol specified tests of hypotheses of the primary endpoints at the planned 2.5% significance level will not be conducted due to early termination of the study prior to enrollment of the planned sample size. Two-sided confidence intervals will be computed at a 95% confidence level but are not intended for inference.

7. Analysis Sets

The following analysis sets are defined for the study.

- Modified Intent-to-Treat (mITT) Analysis Set

The mITT Analysis Set consists of all consented (enrolled) subjects who meet all pre-procedure angiographic eligibility criteria, and in whom treatment with the Enterprise device is attempted.

8. Sample Size Justification

This study was originally planned at a total sample size N=320, with an interim analysis for an early stop (either due to futility or tentative success) at N=160 when subjects were enrolled and followed for a minimum of 6-month post-procedure.

However, as the study will be terminated early due to low enrollment, the total sample size for the descriptive analyses in the final CSR will be based on the actual enrollment achieved. .

9. Data and Safety Monitoring Board (DSMB)

An independent DSMB was constituted for monitoring the accumulated interim data as the study progresses to ensure subject safety. All safety review procedures were established and agreed upon in the DSMB Charter prior to enrollment of the first subject.

10. Analyses to be Conducted

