10.4.4 Safety Follow-up after 12 months post-procedure

AEs that started post the upper bound of 12-Month follow-up (i.e., after Day 451) will be listed.

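### The SAP's planned adverse event summaries leave out angiographic screening failures and the interval from consent to femoral access, and the SAP does not say so

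*SAP*

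**What the plan says.** **Collection.** Protocol 10.5.2 says that the reporting period for entered subjects "begins at the time the study informed consent is signed and ends at the twenty-four month follow-up". For ASFs, protocol 6.1.1, 6.3.1 and 10.5.1 collect AEs from consent until 72 hours after the angiogram or discharge, and longer if an event is unresolved. In protocol Table 1, however, the row "Record of adverse events" has no mark under Screening/Baseline. Its first mark is at pre-treatment on day 0.

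**Reporting promised in the protocol.** Section 9.8 provides a brief safety summary for the ASF set. Section 9.10.4 says of these subjects that "procedural and safety data will be listed and summarized separately from the other analysis populations". The protocol's AE endpoint (3.2.4.3 and 9.6) begins at the start of the index procedure.

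**Reporting planned in the SAP.** Section 10.4.2.2 states that "AEs from the start of the index procedure until completion of the 12-Month Follow-up will be coded". Section 7 defines one analysis set: "The mITT Analysis Set consists of all consented (enrolled) subjects who meet all pre-procedure angiographic eligibility criteria", with the further condition that treatment was attempted. Section 10.4.2 puts every secondary endpoint, AEs included, on that set. The only AE output outside the main window is in 10.4.4: "AEs that started post the upper bound of 12-Month follow-up (i.e., after Day 451) will be listed".

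**The concern.** The collection rules are wider than the SAP's outputs, in both time and population. An ASF cannot be in the mITT set, so an ASF's AE has no place in any AE output that the SAP describes, although the protocol promises one. An AE that starts after consent but before femoral access falls before the SAP window, and the SAP has no pre-procedure counterpart to its late listing.

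Both groups can have exposure that matters. Some ASFs are excluded only at the pre-treatment angiogram, which follows arterial access. Before the procedure, protocol 6.1.3 requires aspirin and an antiplatelet agent ("P2Y12 Platelet Inhibitor: Daily for a minimum of 7 days prior to the procedure"), and part of that period may follow consent. At stake is whether the final report accounts for all the safety data that the protocol required sites to collect.

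**Working it through.** No sample size, power or error rate bears on this point. The check sets collection against reporting, group by group.

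| Group or period | Collected under the protocol? | Output promised in the protocol? | Output described in the SAP? |
|---|---|---|---|
| ASFs, all AEs | Yes, from consent (6.1.1, 6.3.1, 10.5.1); ASF column of Table 1 is marked | Yes (9.8, 9.10.4) | None: outside mITT |
| Entered subjects, consent to femoral access | Yes (10.5.2), but Table 1 is blank at Screening/Baseline | Not in the AE endpoint, which starts at the index procedure (3.2.4.3, 9.6) | None: before the window |
| mITT subjects, pre-treatment angiography in the index session | Yes | Yes | Yes: after femoral access, so in the peri-procedure period |
| Treatment attempted, no device implanted | Yes | Yes | Yes: mITT requires only an attempt |
| Consented, cancelled without an angiogram | Not spelled out: 10.5.1 covers those who had an angiogram, 10.5.2 entered subjects | None specific | None |

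The first two rows are the gap.

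**Is the omission declared?** The SAP states that it drops the hypothesis tests (6, 10.4), the interim analysis (10.5), and the sensitivity, subgroup and site-homogeneity analyses (10.7 to 10.9). It has no such statement for the ASF safety output or for pre-procedure AEs.

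**Table 1.** The protocol-deviation row directly below the AE row is marked at Screening/Baseline. The blank therefore looks specific to the AE row.

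**Late boundary.** SAP 10.1 counts the procedure day as Day 0. Table 2 of the SAP ends at Day 450. Read literally, a listing of events after Day 451 begins at Day 452. Days covered by neither: 452 − 450 − 1 = 1, namely Day 451.

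**Early boundary and imputed dates.** SAP 10.4.2.2 sets a missing onset day to the first of the month. Take an illustrative procedure on the 15th and a post-procedure AE in the same month with unknown day. The imputed Study Day is 1 − 15 = −14, so the event leaves the summary window. A pre-procedure listing would show such records if it flags imputed dates.

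**Size.** The documents give no number of ASFs and no pre-procedure event rate. In the US feasibility study (protocol 1.3.1), 2 of 30 enrolled subjects were disqualified at pre-procedure angiography: 2/30 = 6.7%. This shows that the ASF group need not be empty. It is not a rate of harm. The length of the interval from consent to access is not fixed either: protocol 6.1.1 asks for consent as close to the procedure as possible.

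**The case against.** The strongest reply is that the SAP window is the protocol's own. Sections 3.2.4.3 and 9.6 start the AE endpoint at the index procedure, and the SAP follows them. This stands for the interval from consent to access, where the mismatch begins inside the protocol. It does not answer the ASF gap, because 9.8 and 9.10.4 promise that output separately.

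The table and listing shells and the Close Out Plan are separate documents, not available here, and either might contain a fuller listing. That also stands, so the finding is limited to the SAP text. But the SAP lets the shells change without a new signature, so they do not secure the output.

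Table 1 is a visit grid. The pre-treatment visit could pick up events since consent, and the protocol text states collection from consent in several places. The blank cell is therefore a conflict to reconcile, not proof that events were missed. Day 451 is likewise a wording slip: read by its main clause, the late listing starts after the Day 450 bound.

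A reader might infer more than the documents support:

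- *That the harm goes unreported.* Deaths and serious AEs reach the sponsor within 72 hours (protocol 10.4, 10.8), the DSMB reviews safety data, and SAP 10.2 counts deaths in disposition.
- *That the omission flatters stenting.* ASFs are excluded on angiographic criteria. Both feasibility disqualifications were anatomical (vessel too large, neck too wide).
- *That a full week of premedication per subject is lost.* Consent may come late in that week. Days before consent lie outside AE collection altogether, and events starting after access are summarised.
- *That angiography harm is lost in treated subjects.* Pre-treatment angiography follows femoral access and is inside the window. Only a separate angiogram between consent and procedure would fall outside it.
- *That AEs in subjects cancelled without an angiogram are already in the eCRF.* No rule in the documents says so.

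**Conclusion.** The point holds for two groups: all AEs in ASFs, against an explicit protocol commitment, and AEs in entered subjects between consent and femoral access. Both are absent from the SAP's planned AE summaries, and the SAP does not declare the omission. The ASF part is the firmer of the two.

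The number of events cannot be derived from the documents. The study is closing early with descriptive reporting only, so projecting to the planned 160 or 320 subjects would mean nothing. No primary endpoint is affected, and no direction of bias is shown. The conclusion assumes that neither the shells nor the Close Out Plan already provides these outputs. It is a completeness gap that should be closed before the final report. The Table 1 and Day 451 items are minor.

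**What to change.** 1. **SAP 10.4.2.2:** add one listing, with event and subject counts, of (a) all AEs and serious AEs in ASFs, as protocol 9.10.4 requires, and (b) AEs and serious AEs with onset from consent to the start of the index procedure, in all consented subjects with AE data. Flag imputed onset dates. If the sponsor chooses not to produce it, the SAP should say so and give the reason, as it does for the other dropped analyses.
2. **SAP 10.4.4:** change Day 451 to Day 450, to match the upper bound in Table 2 of the SAP.
3. **Protocol Table 1:** mark AE recording from consent at Screening/Baseline, to agree with 10.5.2. This late in the study it removes the contradiction but cannot recover events that were never recorded.
4. **Subjects cancelled without an angiogram:** state whether their AEs were collected.

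The cost is one extra listing or table, from data that the protocol already requires for ASFs and entered subjects, plus two small text corrections and one clarifying sentence.

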### **10.1.3 Adverse Event Severity and Causal Relationship Ratings**

The Investigator will record the nature, severity, treatment and outcome of the AE, and will determine the relationship to device, procedure or underlying disease. This classification of the event determines the reporting procedures to be followed. The sponsor may upgrade the classification as required for reporting purposes.

For purposes of this protocol, the following definitions will apply.

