10.4 Primary and Secondary Endpoint Analyses

Protocol specified tests of hypotheses of the primary endpoints will not be performed due to the study terminating early for low enrollment. Descriptive analyses of the primary effectiveness and primary safety endpoint will be conducted in the mITT Analysis Set. Categorical data will be summarized with exact binomial confidence intervals for primary effectiveness and safety endpoints. Continuous data will be summarized with averages by visit and as average change from baseline at each visit.

Unless specified otherwise, the classification of adverse events will be based on the data from study case reported forms (CRFs). In the event the data are not captured or are missing, the DSMB and/or CEC adjudication data will be reported.

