10.6 Handling of Missing Data

Unless stated otherwise, missing data will not be imputed, percentages will be based on non-missing data.

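### Related-AE tables rest on the CEC rating alone, with no fallback to the investigator's rating when the CEC rating is missing, so related AEs can only be under-counted

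*SAP*

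**What the plan says.** SAP 10.4.2.2 defines the category first: "AEs related to device/procedure are defined as those with the relationship of definitely, probably or possibility related". It then fixes the source, "Only the relationship as determined by CEC will be used in the safety analysis", and the handling of gaps, "AEs with miss relationship will not be imputed". Related AEs defined this way are tabulated overall and again by study period (peri-procedure, and from then to the 12-month follow-up).

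The protocol provides two ratings for the same event. Under Protocol 10.1.3 the investigator "will determine the relationship to device, procedure or underlying disease". Under Protocol 10.9.1 an independent CEC adjudicates the relationship of AEs, with no restriction to serious events, and its determination is the one to be used in the safety analysis. The SAP's choice of the CEC as source therefore follows the protocol.

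**The concern.** The SAP anticipates that some relationship ratings will be missing, because it states a rule for them. Under that rule an event with no CEC rating cannot enter the related-AE tables, even when the investigator's form records it as definitely, probably or possibly related. The available rating is set aside exactly when it is the only one on file.

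Device- or procedure-related AEs are a named secondary safety output of a single-arm device study with no comparator. A rule that can only reduce that count favours the device. If the CEC-only sentence is also meant to govern the bleeding endpoint, which counts procedure-related hemorrhagic events, the same gap carries over; the SAP does not say whether it does.

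**Working it through.** The plan states no figure on this point, so there is none to reproduce. The check is a trace of the rules, followed by the direction and unit size of the effect.

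**Trace for one event: investigator rating related, CEC rating absent**

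1. Source: only the CEC relationship is used (SAP 10.4.2.2), so the analysis value is missing.
2. Missing values: not imputed (SAP 10.4.2.2), so it stays missing.
3. Definition: a missing value is not definitely, probably or possibly related, so the event is not counted.
4. Result: the event is absent from the related-AE table and from its by-period version. It remains under Any AEs, and under SAEs or AEs leading to death where those apply.

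**Does another provision bring it back?**

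- SAP 10.4 takes AE classification from the CRF by default and adds: "In the event the data are not captured or are missing, the DSMB and/or CEC adjudication data will be reported". That default applies only where nothing else is specified, and 10.4.2.2 specifies something else for relationship. Its substitution also runs from CRF to adjudication, not from the CEC back to the investigator.
- SAP 10.4.2.2 also says "Subjects with multiple relationships on the same AE will be reported by the events of the highest relationship". The sentence restricting the source to the CEC follows in the same paragraph, so this cannot be read as taking the higher of the investigator's and the CEC's ratings.
- SAP 10.6 repeats the general position: "Unless stated otherwise, missing data will not be imputed, percentages will be based on non-missing data".
- SAP 10.7 drops all sensitivity analyses, so no second look is planned.

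None of these restores the event.

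**Direction and unit size**

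Let k of n subjects have at least one related AE when the investigator's rating is used as back-up. Suppose one of the k has a single related AE and the CEC did not rate it.

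- Subject kept in the denominator: k/n − (k − 1)/n = 1/n.
- Subject removed from numerator and denominator, one possible reading of SAP 10.6: k/n − (k − 1)/(n − 1) = (n − k)/[n(n − 1)]. This is positive whenever k < n and, since k is at least 1, no larger than 1/n.

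The rate for the affected subject therefore falls on either reading. Taking 1/n:

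| n | Fall per affected subject |
|---|---|
| 320 (planned total, not reached) | 1/320 = 0.31 points |
| 100 (assumed) | 1/100 = 1 point |
| 50 (assumed) | 1/50 = 2 points |

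If m% of subjects have their only related AE unrated by the CEC, the shortfall is at most m points. The documents give no value for m and no final n.

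Two limits apply. A subject with another related AE that the CEC did rate stays in the subject count, and only the event count falls. And if SAP 10.6 were also applied to remove subjects whose unrated event the investigator considered unrelated, their removal would push the percentage slightly up. The related-AE count is one-directional on any reading; the percentage is so with all mITT subjects in the denominator.

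**The case against.** The strongest reply is that the CEC-only source is the protocol's own prespecified choice in 10.9.1, carried faithfully into the SAP. Because the CEC's remit covers AEs generally, a missing rating would be a failure of execution rather than something the plan builds in. A fallback would mix two kinds of rater in one table. Counting an event as related when both ratings are missing is a worst-case convention that neither document requires. The analysis is purely descriptive, and the primary safety endpoints are untouched: stroke or death uses DSMB-adjudicated data and in-stent stenosis uses the core laboratory.

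Most of this stands, and it limits the size of the point. It does not remove the gap, because the SAP still provides no route for an event that only the investigator has rated. A fallback that leaves the CEC rating primary respects Protocol 10.9.1 for every event the CEC has rated. Protocol 3.1 assigns the same adjudication to a medical monitor, which leaves some doubt about whose rating will be on file.

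A reader might go further than the documents allow in three ways:

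- That the SAP has no rule for missing ratings. It has one, no imputation; what it lacks is a fallback.
- That unrated events are recoded as not related. They are left missing. The table shells are in a separate document, so a row for missing relationship cannot be ruled out.
- That early closure left a backlog of unadjudicated events. The study stopped for low enrollment, SAP 5.4 has treated subjects complete follow-up through 12 months, and nothing in either document reports or expects a backlog.

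**Conclusion.** The point holds: an AE that the investigator rated related and the CEC did not rate is omitted from the related-AE tables, and the omission can only understate related AEs. This follows from the text and needs no assumption about the data.

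The size cannot be established. It is zero if every AE has a CEC rating, and it may well be small given the CEC's general remit. The 1 and 2 point figures are the effect of a single subject at assumed sample sizes. A reader might multiply them into a shortfall of several points, but that would assume a share of unrated events for which the documents give no basis.

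The event stays visible under Any AEs, and under SAEs if serious; no hypothesis test or primary endpoint depends on the rule. The change is worth making because it is cheap and the error runs in one direction, not because it threatens a study conclusion.

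**What to change.** In SAP 10.4.2.2, replace the no-imputation sentence with a source hierarchy:

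1. Use the CEC relationship where it exists, as Protocol 10.9.1 requires.
2. Where it is missing, use the investigator's CRF relationship.
3. Where both are missing, either count the AE as related or show it in a separate row for missing relationship; state in advance which.
4. Footnote the number of AEs classified by each source.

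A cross-reference should make clear that this hierarchy, not the CRF-first default in SAP 10.4, governs relationship.

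The cost is one derivation rule and one footnote. The affected events will carry a different rater from the rest of the table, which the footnote discloses, and the related-AE rate may be slightly higher. If no CEC ratings are missing, the results do not change and the footnote shows it.

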### **3.2.4.3 Adverse Events and Clinical Complications**

Adverse Events (AEs), including complications associated with an untoward medical occurrence, from the start of the index procedure until completion of the 12 month follow-up will be coded using the MedDRA system and summarized with frequencies. Serious adverse events (SAEs), device- or procedure-related AEs, unanticipated adverse device effects (UADEs) and deaths will be presented.

AEs will be presented for the following study periods: 1) peri-procedure – i.e., from the start of the procedure until 24 hours post-procedure; and, 2) through 12 month follow-up – i.e., from 24 hours post-procedure through the 12 month visit or premature termination.

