**Adverse Events and Clinical Complications:**

Adverse Events (AEs), including complications associated with an untoward medical occurrence, from the start of the index procedure until completion of the 12 month follow-up will be coded using the MedDRA system and summarized with frequencies. Serious adverse events (SAEs), device- or procedure-related AEs, unanticipated adverse device effects (UADEs) and deaths will be presented.

AEs will be presented for the following study periods: 1) peri-procedure – i.e., from the start of the procedure until 24 hours post-procedure; and, 2) through 12 month follow-up – i.e., from 24 hours post-procedure through the 12 month visit or premature termination

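### The SAP splits only device- or procedure-related AEs into peri-procedure and follow-up periods, while the protocol requires the split for AEs without restriction by relatedness

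*SAP*

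**What the plan says.** **Protocol.** The study overview (secondary safety endpoint c), Section 3.2.4.3 and Section 9.6 state the same rule. In Section 3.2.4.3 it begins "AEs will be presented for the following study periods: 1) peri-procedure". The first period runs from the start of the procedure to 24 hours afterwards. The second runs from 24 hours to the 12-month visit or premature termination. The sentence just before it lists what is to be reported: "Serious adverse events (SAEs), device- or procedure-related AEs, unanticipated adverse device effects (UADEs) and deaths will be presented". Appendix 1 defines a procedural serious adverse event as an SAE falling between the start of the procedure and 24 hours, with no condition on cause.

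**SAP.** Section 10.4.2.2 says that counts, percentages and "event rates by SOC and PT will be summarized for the following", and then names five event sets: any AEs, related AEs, SAEs, unanticipated AEs and AEs leading to death. All five cover the single span from the index procedure to 12 months. The two periods come in afterwards, for one set: "device or procedure related AEs will be presented overall and by study period as follows", followed by Table 2 with the period bounds. Three further sentences settle what counts as related:

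- "AEs related to device/procedure are defined as those with the relationship of definitely, probably or possibility related"
- "AEs with miss relationship will not be imputed"
- "Only the relationship as determined by CEC will be used in the safety analysis"

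**The concern.** The protocol's by-period display is part of a secondary safety endpoint, and the SAP narrows it to a subset chosen by a causality rating. Take an SAE in the first 24 hours that the CEC rates unlikely or not related, or leaves unrated. Under the SAP text it enters only a total pooled over 12 months. A reader of the planned summaries could not tell how many SAEs or fatal AEs occurred around the procedure. They could tell only how many related AEs did.

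The protocol keeps timing and causality apart: it has a category for procedural SAEs that depends on timing alone. In a single-arm study with no comparator, a timing table that does not first pass through a causality judgement is a useful descriptive complement to the related-event table.

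**Working it through.** No arithmetic applies: the point rests on no sample size, power or event count. The check is a comparison of the two texts.

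1. **Which events the protocol splits.** All three statements of the rule use AEs as the subject ("AEs will be presented for the following study periods" in Section 9.6). The sentence before the rule names related AEs as one of four categories, alongside SAEs, UADEs and deaths. The unqualified term in the next sentence is therefore not shorthand for related AEs.

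2. **Which events the SAP splits.**

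| Event set in SAP 10.4.2.2 | Overall, 0-12 months | By the two periods |
|---|---|---|
| Any AEs | yes | not specified |
| Device- or procedure-related AEs | yes | yes |
| Any SAEs | yes | not specified |
| Unanticipated AEs | yes | not specified |
| AEs leading to death | yes | not specified |

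3. **Whether another SAP section fills the gap.** Section 5.2.2 describes the AE endpoint over one span. Sections 5.4 and 10.4.4 only list AEs that start after the 12-month window. No other section applies these two periods to AEs.

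4. **Who falls outside the split.** Protocol Section 10.1.3 has five causality categories. The SAP counts the top three as related, so the two lowest are outside. An AE with a missing rating does not meet the SAP's definition either, because nothing is imputed. SAP Section 10.4 makes case report form data the default for classifying AEs unless specified otherwise. Section 10.4.2.2 does specify otherwise, so the CEC rating alone decides membership.

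5. **Procedural SAEs.** Counting them as Appendix 1 defines them needs SAEs tabulated by period whatever their cause. The SAP specifies SAEs without period and related AEs with period. Neither table yields the count, and the sentence on related AEs does not ask for a further breakdown by seriousness.

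6. **Whether a reason is given.** Protocol Section 9 says the SAP will reflect the protocol and its amendments. The SAP explains the dropped hypothesis tests (Sections 6 and 10.4) by early termination and the dropped interim analysis (Section 10.5) by the Close Out Plan. It states openly that sensitivity, subgroup and site-homogeneity analyses are omitted (Sections 10.7 to 10.9). Nothing comparable accompanies the narrower AE split. Low enrolment does not explain it by itself, because the split is descriptive and Section 10.1 retains descriptive output.

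**The case against.** Several counter-arguments have force.

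- **Possible drafting slip.** The title of Table 2 and its period bounds refer to AEs generally, and the introducing sentence is worded as an addition. A deliberate restriction is not proved. The sentence is nevertheless explicit, and nothing else in the SAP asks for the wider split.
- **Limited reach.** A possible rating is a low bar in Protocol Section 10.1.3, so an early event drops out only if it is rated in the bottom two categories or is unrated. Use of the CEC rating is itself a protocol rule (Section 10.9.1). This stands. The objection is to using the rating as a filter on the timing table, not to the rating.
- **Other outputs cover part of the ground.** The affected events stay in the overall tables. All deaths and major ipsilateral strokes through 12 months enter the primary safety endpoint whatever their cause (SAP Section 10.4.1.2). Reduced TICI flow during the procedure and acute in-stent stenosis are reported without a relatedness filter. None of these is a by-period table of all AEs or SAEs.
- **Low consequence.** The trial ended early and the report is descriptive. The Close Out Plan is not available here and may address AE displays.

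Three stronger readings are tempting but unsupported. A reader might infer that unrelated events will never be shown by period. SAP Section 10.1 plans listings and Section 11 puts the shells in a separate document, so onset dates may allow single events to be placed. A reader might take the 70.6% of events before discharge in the European registry (Protocol Section 1.3.4) as a measure of what is lost. That figure concerns 17 at least possibly related events (12/17 = 70.6%), a class the SAP still splits, and it uses discharge rather than 24 hours as the cut. Finally, a reader might call timing the main evidence on attribution. No passage says so, and temporal association is already part of the probable rating in Section 10.1.3.

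**Conclusion.** The inconsistency holds as a gap between protocol and SAP. The protocol requires AEs by period without a relatedness limit. The SAP text specifies the split for one of its five event sets and gives no reason. What is missing is a by-period summary of AEs, SAEs and fatal AEs rated unlikely or not related or without a rating, and any count of procedural SAEs as the protocol defines them.

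The number of events concerned cannot be computed from the documents. No confidence interval, endpoint result or success criterion changes, so this is a minor point that is worth correcting because correction is cheap. The conclusion assumes that the SAP text governs the output. It would fall away if the separate shells or the Close Out Plan already provide the wider split.

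**What to change.** In SAP Section 10.4.2.2, change the sentence that introduces Table 2 so that the two-period split applies to any AEs, any SAEs, unanticipated AEs and AEs leading to death as well as to related AEs. The SAE table by period then gives the count of procedural SAEs directly. Align the table shells.

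The period bounds and all five event sets are already defined, so the cost is the existing table run on four more event sets. No new data and no new derivation are needed. If the narrower display is intended, the SAP should say so and justify the departure from Protocol Sections 3.2.4.3 and 9.6.
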